Cover page

Title: Standing Balance as the Fifth Vital Sign in Clinical Setting

NCT04139642

Date: 10/17/2019

Does use of a quantitative balance measurement device influence clinical decision making?

PI: [name], PhD

I. Objective

This 18-month prospective, observational study involving real world data will determine if the use of a standing scale that delivers a quantitative measure of standing balance along with weight (balance + weight) in place of a scale that only delivers weight (weight only) influences clinical decision making by health care practitioners in the ambulatory outpatient setting. Providers will be randomized to receive the balance+weight scale or weight-only scale for 9 months, then to crossover and receive the other for 9 months. The primary outcome measures are (1) providers' self-reported perceptions of whether the balance measurement influences their clinical decision making and (2) the rate of performing falls risk assessments or referring to a specialist for evaluation and treatment based on aggregate billing data. The secondary outcome measure is qualitative interviews with practitioners regarding their perceptions on the utility and barriers to using the device.

II. Background and Rationale

Falls prevention efforts are poised to reduce the significant impact of this high-risk injury, but a critical component for success of a falls prevention program is measurement of risk for falls. While effective measurement is available, barriers prevent implementation due to the need for primary care providers to undertake assessment within the limited time available in the short patient visit.

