The desired population includes practitioners who regularly diagnose and treat patients in ambulatory outpatient settings. We anticipate recruiting 20 clinical practices in which there are physicians, nurse practitioners or physician assistants. In the case where multiple practitioners at a single clinical site choose to participate, the clinic site is treated as a single participant with the primary outcome measures lumped together for all participating practitioners.

3. Measurement / Instrumentation

Immediate feedback from provider on clinical decision-making process. After each patient encounter in which the provider chooses to use the balance measurement feature of the Balance+Weight device based on their own clinical decision-making process, the provider who made a clinical decision regarding balance or falls risk is asked to press a button on a small kiosk that we will provide which logs their agreement with the statement, “The balance measurement influenced my clinical decision making with this patient.”

Data pull of clinic-level diagnosis and referral data. At or just after the crossover between sites has occurred, study personnel in conjunction with the IT departments at participating clinics will pull de-identified aggregated clinic diagnosis and referral data for all participating providers. We will pull this data from both the 9 months of participation in the study, as well as the same 9 month-period in the previous year before the study began as a historical control. The data will be pulled again upon completion of the study for the second 9-month period. The data will include all patients that the provider saw.

Focus group discussions after completion of RCT. Following conclusion of the trial, we will engage all participants in focus groups regarding their experience using the Balance+Weight device.

4. Detailed study procedures

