Recruitment of clinics to participate in study. Study personnel will recruit clinics to participate in an 18-month trial of the quantitative postural control assessment (Balance+Weight) device. Eligible clinics include any that self-report a substantial component of their patient population that may be at risk of falls, but that are not a referral site for patients previously identified as being at elevated falls risk. In clinics where multiple providers see patients, at least one provider must be willing to participate and commit to placing the novel device in their clinic, as well as to the other components of participation detailed below. Due to the number of ambulatory care clinics within a radius to allow same-day servicing of the devices and resource limitations to manufacture units, we will cap recruitment when we reach 20 clinics or 60 devices in service, whichever is reached first. Every participating clinic will have the opportunity to receive the device that delivers Balance+Weight either immediately or after a 9-month waiting period depending on randomization.

Randomization of clinics. A block randomization scheme by clinic type will be used to assign which clinics receive the Balance+Weight device in the first 9 months and which clinics receive the Balance+Weight device in the second 9 months. The block randomization scheme is proposed instead of simple randomization because of the expected variation between clinics in the types of patients they see. Blocks will be determined based on the estimated percent of patients seen who are over 65, diabetic, undergoing chemotherapy (all oncology clinics), or are using assistive devices during some of their care (e.g. orthopaedic trauma clinics). Clinics for whom 50% or more of their patients are in any of these categories will be included in one block, whereas clinics for whom less than 50% of their patients are in any of these categories will be included in the other block. While this scheme does not fully account for the confounder of multiple risk factors for falls or multiple co-morbidities in some clinics, equipoise between treatment arms is also achieved through the crossover design whereby every clinic serves as its own control as well.

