Immediate feedback from provider on clinical decision-making process. After each patient encounter in which the provider assessed balance using the Balance+Weight device, the provider who made a clinical decision regarding balance or falls risk is asked to press a button on a small kiosk that we will provide which logs their agreement with the statement, "The balance measurement influenced my clinical decision making with this patient." These kiosks from Happy-Or-Not.com are completely wireless and use their own 3G network to communicate the results of a single 4-point Likert scale question back to a central server that the study staff can monitor to collect data and get a real-time indication of whether the providers are using the Balance+Weight device.

Crossover of sites after 9 months. At the 9-month point, study personnel will go to every site to reprogram each device from Balance+Weight mode to Weight Only mode or vice versa, and to move the immediate feedback kiosks to the new Balance+Weight sites.

Data pull of clinic-level diagnosis and referral data. At or just after the crossover between sites has occurred, study personnel in conjunction with the IT departments at participating sites will pull the clinic diagnosis and referral data for all participating providers. After Casey et al.[15], our initial plan is to count instances of the following Common Procedural Terminology Category II codes:

- (Primary) CPT II 3288: Assessment of falls risk
- CPT II 0518: Development of a falls care plan
- CPT II 1101: Documentation of falls in past year (no falls/ single fall without injury)
- CPT II 1100: Documentation of an injurious fall/ multiple falls
- Other referral codes as appropriate

Because CPT codes are updated each calendar year, we will review the new codes each year and revise this code list as new codes related to falls assessment are added or subtracted. We will pull this data from both the 9 months of participation in the study, as well as the same 9 month period in the calendar year before the study began as a historical control. The data will be pulled again upon completion of the study for the second 9-month period.

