Focus group discussions after completion of RCT. Following conclusion of the trial, we will engage all participants in focus groups regarding their experience using the Balance+Weight device. These discussions are intended to complement and enrich our understanding of how the users of the device (providers and medical assistants) either benefitted or did not benefit from having it in the clinic. Feedback will be used to assess the implementation toolkit and inform the development of the final version of the toolkit. Seed questions for these focus groups include:

- In what ways, if any, did you find having a quantitative postural control assessment on every patient useful in your clinical decision making?
- If you applied the device's data differently for different patients, how did you use it across these different patients?
- Did the time it took to make the measurement or interpret the measurement impact the efficiency of your clinic (positively or negatively) and how?
- In what ways could we better implement and train you to use the device, and use it with the electronic medical record?

5. Internal Validity

As described above in section D, we use randomization and a crossover design to assure equipoise between the two arms of the study. All statistical analyses described below in section F will be performed by blinded analysts to mitigate the chance of bias. Given that the study uses real world data with commercially available devices in true clinical settings, the external validity of the study results is expected to be excellent.

6. Data Analysis

Statistical analysis of kiosk data. The kiosk data will be analyzed by tabulating the frequencies of scores by kiosk (0-3) and performing a weighted kappa analysis to determine if providers agree upon whether the balance measurement influenced their clinical decision making. The proportion of decisions across all providers where the balance measurement positively influenced the decision-making process (top two options) and its 95% confidence interval will be calculated.

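### The weighted kappa planned for the kiosk outcome has no paired ratings to work on; the confidence interval for the top-two proportion also lacks a method that respects the clinic as participant

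*Combined protocol and SAP*

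**What the plan says.** Section I makes providers' "self-reported perceptions of whether the balance measurement influences their clinical decision making" the first of two primary outcomes, and III.1 repeats this.

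The data come from kiosks. Under III.4 (immediate feedback), after an encounter in which balance was measured, "the provider who made a clinical decision regarding balance or falls risk is asked to press a button on a small kiosk". The press records how far that provider agrees that the measurement influenced his or her own decision for that patient. The kiosks "communicate the results of a single 4-point Likert scale question back to a central server". At nine months, staff visit the sites "to move the immediate feedback kiosks to the new Balance+Weight sites".

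Section III.6 lists three analyses of these data: frequencies of the 0-3 scores by kiosk; "performing a weighted kappa analysis to determine if providers agree upon whether the balance measurement influenced their clinical decision making"; and the proportion of decisions, pooled over all providers, that fall in the top two options, with a 95% confidence interval. It gives no weights or pairing rule for the kappa and no method for the interval.

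On the unit of participation, III.2 says that where several practitioners at a site take part, "the clinic site is treated as a single participant with the primary outcome measures lumped together for all participating practitioners".

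**The concern.** Kappa measures agreement between raters on the same items. Here each press appears to rate a different item: another patient, and the presser's own decision. If so, a listed analysis of a primary outcome cannot be run, and the plan has no other means of supporting a statement that providers agree. A substitute chosen once the scores are visible would be post hoc. A kappa computed by lining up unrelated presses would be worse, because it would produce a number that looks like agreement and is not.

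The second, smaller concern is the interval. Presses from one clinic share providers, case mix and habits of use, so they are unlikely to be independent. Section III.6 does not say how, or whether, the interval will allow for this.

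**Working it through.** **Is there anything to pair?** The plan states no target kappa, kiosk sample size or precision, so there is no figure of its own to reproduce. The check is structural.

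- Raters per encounter: one, the deciding provider (III.3, III.4).
- Item rated: that provider's own decision for one patient, so it changes with every press.
- Content sent: one 4-point answer. No provider, patient or encounter identifier is described.
- Tabulation: score counts by kiosk (III.6), which are marginal totals only.

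No section describes a second rater, a shared set of patients or a repeat rating. This absence is inferred from the procedure; no sentence states it. Multi-rater forms of kappa fail for the same reason.

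**What a forced kappa would show.** Weighted kappa = 1 - (observed mean disagreement) / (chance-expected mean disagreement), and the observed term needs the joint table. As an illustration with assumed counts, take two kiosks with 200 presses each and identical scores 0/1/2/3 of 20/40/80/60, that is, proportions 0.1/0.2/0.4/0.3.

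- Linear weights, expected: 2 × (0.02×1 + 0.04×2 + 0.03×3 + 0.08×1 + 0.06×2 + 0.12×1) = 1.02.
- Sorted pairing: observed 0, kappa = 1.00.
- Reverse-sorted pairing: observed (20×3 + 40×2 + 40×2 + 20×3)/200 = 1.40, kappa = 1 - 1.40/1.02 = -0.37.
- Quadratic weights: expected 1.78; reverse-sorted observed (20×9 + 40×4 + 40×4 + 20×9)/200 = 3.40, kappa = 1 - 3.40/1.78 = -0.91; sorted 1.00.
- Over 5,000 random pairings the mean is 0.00 (95% range about -0.10 to 0.10 linear, -0.14 to 0.13 quadratic).

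Two kiosks with exactly the same distribution can therefore show perfect agreement, none, or worse than chance.

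**The interval.** The documents give 20 clinics as the planned number (III.2; III.4 adds "we will cap recruitment when we reach 20 clinics or 60 devices in service, whichever is reached first") but no press count, expected proportion or intraclass correlation (ICC). Assumed: 20 equal clinics, 50 presses each, 70% in the top two options.

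- Independent presses: 1.96 × √(0.7 × 0.3 / 1000) = 2.84 percentage points.
- Design effect: 1 + (50 - 1) × ICC.
- Adjusted half-width: multiplier × √(0.21/1000) × √(design effect), with multiplier 1.96 or t on 19 df (2.093).
- Approximate coverage of the independent-press interval: 2Φ(1.96/√(design effect)) - 1.

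| ICC | Design effect | Half-width, 1.96 (points) | Half-width, t on 19 df (points) | Coverage if presses treated as independent |
|---|---|---|---|---|
| 0.01 | 1.49 | 3.5 | 3.7 | 0.89 |
| 0.05 | 3.45 | 5.3 | 5.6 | 0.71 |
| 0.10 | 5.90 | 6.9 | 7.4 | 0.58 |
| 0.20 | 10.80 | 9.3 | 10.0 | 0.45 |

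Unequal clinics were simulated (beta-binomial, gamma press counts with mean 50 and coefficient of variation 1, 20,000 runs). Results are in the same ICC order.

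- 1.96 × SD of the pooled proportion: 4.0 / 6.8 / 9.2 / 12.6 points.
- Coverage, presses treated as independent: 0.84 / 0.59 / 0.46 / 0.34.
- Coverage, standard cluster-robust with t on 19 df: 0.92 / 0.92 / 0.91 / 0.90.
- Coverage, bias-reduced (CR2) variance with Satterthwaite df (mean 9.9): 0.95 / 0.94 / 0.93 / 0.93.
- Mean CR2 half-width, from a separate shorter run: about 4.4 / 7.3 / 9.8 / 13.6 points.

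**The case against.** The best defence of the kappa is that the word was used loosely, for consistency of scores across kiosks. That does not rescue it. The stated purpose is to find out whether providers agree, and similar distributions are not agreement. Differences between kiosks would also reflect case mix, which the plan itself expects (it blocks the randomization "because of the expected variation between clinics in the types of patients they see"), and each clinic's free choice of whom to measure.

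A second defence is that little depends on it: no target kappa, test or decision rule is attached, and the primary question is addressed by the frequencies and the proportion. This stands, and it limits the seriousness. Even so, those summaries describe only rated encounters, where the provider chose to measure balance and made a decision about balance or falls risk.

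On the interval, the plan is silent; it does not say that a plain binomial interval will be used. The narrowness is conditional, and its size rests wholly on assumed inputs. Tabulating by kiosk keeps some site information, though not in the interval. Taken alone this is missing detail, and it would not justify the rating given below.

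**Conclusion.** The concern holds. Paired ratings described: zero. The weighted kappa cannot be validly computed from the data the kiosks will collect, and it cannot support any statement on whether providers agree. Confidence in this is high, because the two descriptions of the procedure are consistent and nothing elsewhere supplies a second rating. What is lost is a supporting statement; the score distribution and top-two proportion survive for rated encounters. It should be fixed before the scores are seen, because it is a listed analysis of a primary outcome.

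The interval point is secondary. Its direction is certain for any positive within-clinic correlation if presses are treated as independent. Its size is unknown. The illustration (2.8 points against 3.7 to 10.0 with t on 19 df, equal clinics) depends on the assumed press count, proportion and ICC. It affects stated precision only.

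**What to change.** In III.6:

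1. Delete the kappa and the claim attached to it.
2. Report the 0-3 distribution and the top-two proportion for each clinic, with the range and a between-clinic SD or ICC. Call this between-clinic variation in reported influence. State that it mixes case mix, choice of patients measured and provider views, and does not measure agreement on the same encounter.
3. Keep the pooled proportion as the estimate, described as applying to rated encounters. Name a 95% interval clustered by clinic with a small-sample correction, for example CR2 variance with Satterthwaite t degrees of freedom. Generalized estimating equations with a small-sample correction would also do.
4. Use the clinic as the cluster, combining all kiosks at a clinic. Assign each press by kiosk location and period: kiosks move at crossover, so a table by physical kiosk could mix two clinics.

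If an unweighted mean over clinics is also reported, label it as a different quantity. If agreement on the same encounter is wanted, it needs new data, such as a subset of encounters rated by two providers.

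The cost is three or four sentences and a log of which kiosk stood where in each period, with no new data collection. The downsides are a wider interval, coverage that may fall slightly below nominal with about 20 unequal clinics (0.93 to 0.95 in the simulation), and same-encounter agreement left unanswered.

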Training of clinics. At delivery of the Balance+Weight device to the clinic, a one-hour in-service will be performed by study personnel to train all providers and medical assistants on its proper use and the entry of data into the electronic medical record. This training will include how to operate the device and how to use the accompanying documentation with the reported data to inform clinical decision-making. This documentation will include threshold values for likelihood of the patient's balance being Within Normal Limits as well as the change in value that would indicate a change in the patient's balance status along with appendices that contain the published peer-reviewed journal articles upon which these recommendations are based. Upon request by the clinic, study personnel will repeat the training if refreshers are needed by clinic staff. An unlimited number of refresher trainings are permitted for each clinic, and the number of trainings requested per clinic will be recorded.

Incorporation of quantitative postural control assessment device into clinic flow including immediate feedback on clinical utility. Each participating clinic will place the study device in a location to allow its use instead of their weight scale. In the Balance+Weight arm, the device is capable of either just giving weight, or of providing balance data if the patient stands quietly with eyes closed for 30s. In the Weight Only arm, the device only gives a weight measurement, just as a standard weight scale would. In both

cases, the provider and their staff make their own clinical decisions as to which patients to make measurements of and how to use the provided information. The medical assistant may choose to enter the appropriate values into the medical record and continue with any other standard procedures in that clinic setting as part of the rooming or initial evaluation process. The provider can then examine the recorded balance measurement along with their standard examination and determine whether any further evaluations in that clinic or referral to a specialist, physical therapy, or other falls prevention is appropriate and record that diagnosis or referral into the medical record.

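### The first primary outcome pools kiosk presses across all providers into one proportion with a 95% confidence interval, and no allowance for clustering by clinic is stated

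*Combined protocol and SAP*

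**What the plan says.** Provider self-report through the kiosk is the first of two primary outcomes (Section I; III.1). Its analysis is set out in III.6 under kiosk data: score frequencies by kiosk, a weighted kappa, and the headline figure, "The proportion of decisions across all providers where the balance measurement positively influenced the decision-making process (top two options) and its 95% confidence interval". No method for the interval is given.

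Other sections describe the structure of the data:

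- **Unit.** Where several practitioners at one site take part, III.2 says "the clinic site is treated as a single participant with the primary outcome measures lumped together for all participating practitioners".
- **Number of units.** III.4 (recruitment) says "we will cap recruitment when we reach 20 clinics or 60 devices in service, whichever is reached first". There are therefore at most 20 clinics, and there could be fewer.
- **Heterogeneity.** III.4 (randomization) justifies blocking by the "expected variation between clinics in the types of patients they see".
- **Use of the device.** III.4 (clinic flow) says "the provider and their staff make their own clinical decisions as to which patients to make measurements of", so press counts may differ widely between clinics.
- **When to press.** III.3 opens its instruction with "After each patient encounter in which the provider chooses to use the balance measurement feature of the Balance+Weight device". III.3 and III.4 both then say that "the provider who made a clinical decision regarding balance or falls risk is asked to press a button on a small kiosk".

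**The concern.** Presses by the same providers in the same clinic are unlikely to be independent. Some providers will find the reading useful more often than others, and clinics see different patients. A binomial interval counts every press as a separate piece of evidence, so it shrinks as presses accumulate. The real information is limited by the number of clinics.

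The stake is the stated precision of a primary outcome. This interval is the only statement of uncertainty planned for it. Unequal press counts would make matters worse, because a few heavy-use clinics would dominate the pooled figure while the interval still looked tight.

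A smaller, separate matter is the press instruction. Its second half may only identify who presses. It may also mean that a reading which led to no balance or falls decision gets no press. Clinics could apply it differently.

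**Working it through.** **Plan's own figure.** The documents state no sample size, expected press count, precision or ICC for the kiosk outcome, so there is no kiosk figure to reproduce. The billing paragraph of III.6 does give encounter volumes, and these reproduce: 360/0.19/16/3 = 39.47 encounters per provider-month; × 10 providers × 9 months = 3,552.6; doubled = 7,105.3. Twenty clinics with 9 months each on Balance+Weight is the same 180 provider-months, if each clinic has one provider. Balance+Weight encounters per clinic are then 7105/20 = 355.25.

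**Assumptions not in the documents.** K = 20 clinics contributing presses, one provider per clinic, true proportion p = 0.60 (so p(1−p) = 0.24), presses at 5%, 10% or 25% of encounters, and ICC 0.01 to 0.10.

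**Formulas.** Here m is presses per clinic and N = 20m.

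- Usual half-width: 1.96 × √(0.24/N)
- Design effect: DE = 1 + (m − 1) × ICC
- Clustered half-width: t(0.975, 19 df) × √(DE × 0.24/N), with t = 2.093
- Coverage of the usual interval: 2Φ(1.96/√DE) − 1

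**Worked case, 5% presses, ICC 0.05.** m = 17.76 and N = 355.25. Usual: 1.96 × √(0.24/355.25) = 0.0509. DE = 1 + 16.76 × 0.05 = 1.84. Clustered: 2.093 × √(1.84 × 0.24/355.25) = 0.0738. Coverage: 2Φ(1.446) − 1 = 85%.

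**Equal press counts, ICC 0.05:**

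| Presses (% of encounters) | m | N | DE | Usual ± (points) | Clustered ± (points) | Coverage of usual |
|---|---|---|---|---|---|---|
| 5% | 17.8 | 355 | 1.84 | 5.09 | 7.38 | 85% |
| 10% | 35.5 | 710.5 | 2.73 | 3.60 | 6.35 | 76% |
| 25% | 88.8 | 1,776 | 5.39 | 2.28 | 5.65 | 60% |

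**Other ICCs.** At 0.01 with 5% presses: DE 1.17, 5.09 against 5.88 points, coverage 93%. At 0.01 with 25% presses: DE 1.88, 2.28 against 3.33 points, coverage 85%. At 0.10: coverage 77% with 5% presses and 47% with 25%.

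**Simulation** (beta-binomial, 20,000 runs, 20 clinics, ICC 0.05). With equal counts, the usual interval covers about 84%, 77% and 60%, which agrees with the formula. With lognormal press counts of coefficient of variation 1, it covers about 78% (5% presses) and 50% (25% presses). A cluster-robust interval for the same pooled proportion, with t on 19 df, covers about 92% in both of those cases.

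**The case against.** **Silence does not show that a binomial interval will be used.** This stands. A reader might infer that the sponsor has chosen an interval that ignores clustering. The documents do not say so; they only leave the method open. The point is conditional on the usual default, but a primary analysis should name its interval.

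**The outcome is descriptive.** No test, threshold or power claim is attached to it, and frequencies by kiosk would expose dominant or discrepant clinics. That limits the consequence. However, neither the frequencies nor the kappa is said to enter the interval.

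**The clinic is not always the stated unit.** Section I and III.1 speak of randomizing providers. Repeated presses by one provider are correlated too, so the problem remains.

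**A reader might infer that the kiosk proportion overstates influence per balance reading, and that a press should follow every reading.** The documents do not support this. III.6 makes decisions the denominator, and the press instruction can be read consistently with that. Influence per reading is a quantity the plan never set out to estimate, and a press after every reading would replace its denominator. What remains is an unclear instruction whose effect cannot be sized from the documents.

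**A reader might also conclude that the mean of clinic proportions should become the headline.** It matches the unit in III.2, and its t interval covers about 95% when press volume and answers are unrelated. But it weights a clinic with one press like one with hundreds, so it estimates something other than the pooled proportion. In simulation with coefficient of variation 1 and ICC 0.05, press count and clinic answer were correlated at 0.3. The clinic-mean interval then covered the pooled figure about 92–93% of the time (5% presses) and 87–88% (25% presses). At correlation 0.5 it covered about 86% and 71%. The cluster-robust interval stayed at about 91–92%.

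**Conclusion.** The point holds as an unspecified interval for a primary outcome whose data are clustered by the plan's own description. If the usual binomial interval is used, the kiosk result will look more precise than 20 or fewer clinics allow. At ICC 0.05, the clustered half-width is about 1.4 times the usual one with 5% presses (7.38/5.09) and about 2.5 times with 25% (5.65/2.28). The effect is minor if the ICC is near 0.01 and presses are few.

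These sizes rest on assumed values for the ICC, press share, proportion and spread of press counts. Only the encounter volume comes from the documents, and it was given there for the billing outcome. The direction does not depend on those values, provided that the within-clinic correlation is positive and clinics log more than one press each. The change should be made; it does not call the design itself into question.

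**What to change.** 1. **Interval (III.6, kiosk data).** Keep the pooled proportion of decisions as the headline. State that its 95% interval uses clinic as the cluster, with a cluster-robust variance, a small-sample correction and t on (clinics with at least one press) minus 1 degrees of freedom. With x_i top-two presses out of m_i in clinic i, K such clinics, and p̂ = Σx_i/Σm_i, the standard error is √[K/(K−1) × Σ(x_i − p̂m_i)²] / Σm_i. Coverage with very unequal press counts is about 91–92%, slightly short of nominal, and the report should say so.
2. **Sensitivity analysis.** Report the mean of the clinic proportions with its t interval. Note that it weights clinics equally and estimates a different quantity.
3. **Description.** Call the result a proportion of logged decisions, not of all balance readings. The number of readings may not be recoverable from the record, since "The medical assistant may choose to enter the appropriate values into the medical record" makes entry optional.
4. **Minor clarification (III.3 and III.4).** State whether a reading that led to no balance or falls decision gets a press, so that every clinic uses the denominator in III.6.

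The cost is a wider stated interval, slightly more analysis work and one clearer sentence in the kiosk instruction. Recruitment, randomization and data collection otherwise stay as they are.
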